Why do so many patients still progress to ESRD? There is growing evidence implicating proteinuria as a major player in the development of progressive tubular injury, interstitial fibrosis, and GFR loss. The higher the sustained levels of proteinuria, the faster the decline in renal function,¹⁵ a relationship that is true not only for patients with IMN but for other proteinuric renal diseases including FSGS and diabetic nephropathy.¹⁶⁻¹⁹ The reverse appears also to be true. There is strong evidence to support that remission of proteinuria (either complete or partial remission) is a valid surrogate end point for both improved renal survival and slower rate of progression of renal disease, and that this reduction is an important therapeutic target for the clinician. This view is in line with the position statement of the NKF and NIDDKD indicating that proteinuria can be used as a surrogate marker and principal endpoint in clinical trials in proteinuric renal disease where GFR-based declines in function take too long to be of practical use.²⁰ Proteinuria is also a marker for CV risk.^{5, 21-24} Recent post-hoc analyses of the diabetic trials RENAAL, IDNT and others, have shown that proteinuria determines renal outcome^{25, 26} and CV outcome.²⁷⁻²⁹ The link between chronic renal failure (CRF) and CV disease is so strong that over 40% of patients starting dialysis already have evidence of CV disease.^{30, 31} This information is important in the present study since all patients will have high grade proteinuria >5 g/24h, a scenario almost universally associated with marked abnormalities in their lipid profile (high total cholesterol, normal or low levels of HDL and increased LDL).^{5, 6} Apart from hyperlipidemia, patients with IMN and nephrotic syndrome (NS) are also at risk for thromboembolic events, with prevalence rate as high as 50% and a mortality rate within this group as high as 42%.^{4, 32} These data serve to emphasize the importance of other common life-defining sequelae of membranous nephropathy in these patients, in addition to their risk of renal failure.

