After the second course of RTX therapy at six months they will have no further RTX therapy regardless of their proteinuria level
3. Significant potential life threatening infection.
4. Persistent elevation of liver enzymes >2 x normal (despite CSA arm dose reduction).
5. Persistent elevation of serum potassium >6.0 mEq/l despite diet changes, ACEi/ARB reduction, diuretic dose increase (and in the CSA arm dose reduction).
6. A rise in serum creatinine by $>30\%$ above baseline that persists in the absence of secondary causes such as volume depletion or use of potential nephrotoxic agents (and despite adjustments in the CSA dose)
7. Persistent hypertension in either arm, i.e. supine blood pressure >160 mmHg systolic or >90 mmHg diastolic, despite institution of maximum antihypertensive therapy (and despite adjustments of CSA dose)

8. Other clinically relevant adverse effects not resolved by reduction in dosage of test medications.
9. Development of any malignancy or lymphoproliferative disorder.
10. Pregnancy.
11. The appearance of an independent disease whose standard therapy requires continuous administration of significant amounts of corticosteroids, other immunosuppressive agents or plasma exchange therapy.
12. Serious concomitant disease with an expected survival of less than 4 years.
13. At the wish of the patient.
14. The study will be placed on hold if 3 of the first 5 patients enrolled and treated with RTX or CSA develop severe opportunistic infections, or experience Grade 3-4 SAEs.

Patients who choose to discontinue study medication or are withdrawn because of adverse events will be strongly encouraged to continue follow up examination to the study termination.

Ancillary studies:

1. DNA Testing

Recent data show that in patients with membranous nephropathy, mutations in HLA-DQA1 and PLA2R1 alleles are associated with an increased risk for developing membranous nephropathy.⁸⁰ One of these alleles, the PLA2R1, is in fact the gene for the PLA2 receptor. In our pilot studies, ~70% of the patients with membranous nephropathy had antibodies present in circulation against PLA2 receptor.⁷⁷ Thus we would like to evaluate a linkage between the presence of these antibodies and potential genetic mutations in this group of patients. We will ask for the patients consent to further evaluate this linkage by collecting samples of blood to perform additional testing as part of their informed consent form (ICF).

2. Quantitative gene expression analysis

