Adverse events (both patient and event counts) will be tabulated by body system, severity and, for each severity, by investigator-assessed relationship to study drug. Group comparisons for adverse events with 4 or more occurrences will be done using chi-square or Fisher's exact test. The last RTX injection is at 6 months and the tapering of Cyclosporine will be completed by the end of month 14. Hence, the adverse events analyses will focus on events through month 18, allowing these additional months for potential lingering Cyclosporine or RTX complications.

The analysis of the primary endpoint (urine protein failure at month 24) will be intent-to-treat (ITT), and will include all randomized subjects in the analysis. For those without a 24 month visit, the 18 month visit results will be used if available, otherwise they will be assumed to have failed at 24 months. Per protocol (PP) analyses will also be done including only those subjects who receive a full course of study medication and who have a 24 month visit.

Interim analyses: No interim analyses for efficacy will be performed during the trial, however safety data will be compiled and reviewed approximately every six months or at the request of the Data and Safety Monitoring Board.

Investigator and Coordinator Training: In order to make efficient use of funding, annual investigator and coordinator meetings will be coordinated with national nephrology meetings where possible. It is expected that the majority of the training will occur through web-based technology and will be coordinated through the data management and coordinating Center.

The **Data Management and Coordinating Center (DMCC)** is located at the Applied Health Research Center (AHRC) at St. Michael's Hospital/University of Toronto. The DMCC will be responsible for facilitating all aspects of the study planning, training, implementation, data collection and analysis.

The clinical information collected for this study will be stored at the DMCC at the Applied Health Research Centre of St. Michael's Hospital in Toronto, ON, Canada and also sent to a federal data repository held by the Office of Rare Diseases Research (ORDR) and located at the University of South Florida (USF) in Tampa, FL.

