An unexpected adverse event is defined as any adverse experience...the specificity or severity of which is not consistent with the risks of information described in the protocol or product monograph.

Expected adverse events are those that are identified in the research protocol or product monograph as having been previously associated with or having the potential to arise as a consequence of participation in the study.

All adverse events that occur between Time 0 and study termination will be reported. All reported adverse events will be classified using the current version of the Common Terminology Criteria for Adverse Events (CTCAE) developed and maintained by CTEP at National Cancer Institute.

- Within **24 hours** (of learning of the event), investigators must report any Serious Adverse Event (SAE) that:
 - Is considered life-threatening/disabling or results in death of subject
 - OR-
 - Is Unexpected/Unanticipated
- Investigators must report all other SAEs within **5 working days** (of learning of the event).
- All other AEs must be reported to the DMCC within **20 working days** of the notification of the event or of the site becoming aware of the event.

Local institutional reporting requirements to IRBs, any GCRC oversight committee and the FDA, if appropriate, remain the responsibility of the treating physician.

As part of the reporting structure, SAEs will be reported to Health Canada, Genentech Drug Safety and the Genentech medical science liaison. An adverse event summary form will be completed and will be summarized for each IRB and Health Canada annually.

Sites will enter all Adverse Event data into the study eCRF. Upon entry of a serious adverse event, the system will notify the DMCC by email. The DMCC will in turn notify the study PIs, the designated medical monitor and any other designated personnel by email. The medical monitor will then review the SAE data to determine causality (definitely not related, probably not related, possibly related, probably related, definitely

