related) of the serious adverse event. The medical monitor [and, if applicable, sponsor] may request further information if necessary and possibly request changes to the protocol or consent form as a consequence of the serious adverse event. A back-up notification system is in place so that any delays in review by the medical monitor beyond a specified period of time are forwarded to a secondary reviewer. The eCRF maintains audit trails and stores data (and data updated) related to any adverse event in the study.

Study Discontinuation

The Study Sponsor, DSMB and local IRBs (at their local site) have the authority to stop or suspend this trial at any time. This study may be suspended or closed if:

- Accrual has been met
- The study objectives have been met
- The Study Investigators believe it is not safe for the study to continue
- The DSMB suspends or closes the trial

Subject Discontinuation

An intent to treat approach will be used. All data acquired prior to termination for the reasons outlined below will be included in the primary analysis unless patient withdraws consent. Every effort will be made to conduct a final study visit with the participant and participants will be followed clinically until, if applicable, all adverse events resolve.

Reasons for subject discontinuation include:

- Withdrawal of consent
- Withdrawal by the participant
- Withdrawal by the investigator
- Intercurrent illness or event that precludes further visits to the study site

Regulatory issues:

1. Inclusion of women: Women make up approximately 30-50% of the population of patients with IMN and are expected to be enrolled in numbers in proportion to this normal distribution.
2. Inclusion of minorities: Individuals of all races and ethnicities are at risk for MN. Based on the ethnic composition of the patients followed at, and referred to the Mayo Clinic the population served will include African-Americans, Asian, and Hispanic subjects proportional to that in the general US and Canadian population. This will ensure adequate enrollment within the different racial groups.

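### The mandatory early safety hold counts SAEs of Grade 3 or 4 only, so a patient whose only qualifying event is a fatal SAE other than an opportunistic infection does not count toward it

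*Combined protocol and SAP*

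**What the plan says.** The rule is item 14 under Stopping points for medications: "The study will be placed on hold if 3 of the first 5 patients enrolled and treated with RTX or CSA" meet a qualifying condition, namely that they "develop severe opportunistic infections, or experience Grade 3-4 SAEs". It is worded as mandatory and has two limbs. The infection limb carries no grade limit. The SAE limb is limited to two grades.

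Under Protection for Human Subjects, Adverse event reporting, all events are classified by the current CTCAE version, but the grade definitions are not printed. The same section defines serious events with death and life-threatening events as separate criteria. It requires 24-hour reporting of an SAE that "Is considered life-threatening/disabling or results in death of subject". Neither provision is linked to the item 14 count.

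Other routes to a halt are discretionary. Study Discontinuation says that the sponsor, DSMB and local IRBs "have the authority to stop or suspend this trial at any time". The list of grounds there, which includes investigators believing the trial unsafe, opens with "This study may be suspended or closed if". Under Interim analyses, "safety data will be compiled and reviewed approximately every six months" or when the DSMB asks. The DSMB section schedules semi-annual calls and says that a charter is still to be developed.

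**The concern.** A rule meant to remove discretion early in the trial should not leave out the most severe outcome. Read literally, item 14 counts a non-fatal Grade 3 SAE but not a fatal pulmonary embolism in a patient with no earlier qualifying event. Deaths that are not infections are foreseeable in this disease: Background and Significance gives a thromboembolic prevalence of up to 50% and a mortality of up to 42% among those affected. No time frame is given, so these figures are not an early event rate. They show only that such deaths are not a remote possibility.

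What is at stake is whether the one numeric, mandatory trigger fires when it should. Every other safeguard that covers deaths is a reporting duty or a power that someone must choose to use.

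**Working it through.** The plan gives no operating characteristics for this rule, so there is no stated figure to reproduce.

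**Who counts, from the text**

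| Patient's event(s) | Counted by item 14? |
|---|---|
| Severe opportunistic infection, fatal or not | Yes, this limb has no grade limit |
| Grade 3 or 4 SAE | Yes |
| Grade 3 or 4 SAE, then death | Yes, through the earlier SAE |
| Fatal SAE only, not an opportunistic infection | No, if death is graded above 4 |

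**Counting, with no rates assumed** (the threshold is read as at least 3 of 5)

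- Two patients with Grade 3 or 4 SAEs plus one such death: the count is 2 as written, so no hold; with death included it is 3, so hold.
- Three or more such deaths: at most 5 − 3 = 2 patients remain to be counted, so the rule as written cannot fire.

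**Probabilities, with assumed rates**

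Let q be the chance that a patient has an event counted as written. Let f be the chance that a patient's only qualifying event is a fatal SAE other than an opportunistic infection. The documents give neither, so both are assumed, and patients are taken as independent.

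- As written: P(hold) = P(Bin(5, q) ≥ 3)
- With death included: P(hold) = P(Bin(5, q + f) ≥ 3)

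For example, at q = 0.10 as written: 10(0.1)³(0.9)² + 5(0.1)⁴(0.9) + (0.1)⁵ = 0.0081 + 0.00045 + 0.00001 = 0.0086.

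| q | As written | f = 0.01 | f = 0.02 | f = 0.05 |
|---|---|---|---|---|
| 0.10 | 0.0086 | 0.0112 | 0.0143 | 0.0266 |
| 0.20 | 0.0579 | 0.0659 | 0.0744 | 0.1035 |
| 0.30 | 0.1631 | 0.1766 | 0.1905 | 0.2352 |

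At q = 0.10 the increase is 0.3, 0.6 or 1.8 percentage points. At q = 0.30 and f = 0.05 it is 0.2352 − 0.1631 = 7.2 points.

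**Given that exactly one such death has occurred**

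The other four patients must supply 3 counted events as written, or 2 with death included. Here q applies to each of those four.

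| q | As written, P(Bin(4, q) ≥ 3) | With death, P(Bin(4, q) ≥ 2) |
|---|---|---|
| 0.05 | 0.0005 | 0.0140 |
| 0.10 | 0.0037 | 0.0523 |
| 0.20 | 0.0272 | 0.1808 |

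For example, at q = 0.10: 4(0.1)³(0.9) + (0.1)⁴ = 0.0037, against 1 − 0.6561 − 0.2916 = 0.0523.

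**The case against.** The strongest objection is that the gap depends on a grading scale the documents do not print. If 4 were the top grade, death would already be inside the range and nothing would be missing. That stands as a condition on the conclusion: under that reading the gap is zero. The protocol does, however, treat death and life-threatening events as distinct outcomes in its SAE definition, and it names death outright in the reporting rule. Item 14 does neither, so a site would have to look outside the protocol to learn whether a death counts.

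The second objection is that other safeguards cover the gap. Deaths reach the coordinating center, the PIs and a medical monitor quickly, a back-up reviewer exists, the DSMB can call for a safety review between scheduled ones, and several bodies can suspend the trial. Three uncounted deaths in five patients would pass unnoticed only if all of these failed. This stands as a limit on the practical harm. It does not repair the rule, because none of these is a mandatory numeric trigger.

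Third, the rates are assumed, and the larger contrasts apply only once a death has occurred. The thromboembolism figures have no time frame. Concomitant Treatment advises considering prophylactic anticoagulation in the most nephrotic patients, and Toxicity of Rituximab reports no major drug-related event in the two pilot studies. All of this is fair and supports a minor rating.

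Finally, the wording is most likely a slip, and everyone would count a death in practice. That is plausible, and the documents give no reason for leaving deaths out. It is an argument for correcting the text.

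**Conclusion.** The concern holds as a minor error in a stated safety rule. It rests on one assumption, that the CTCAE version in use grades a fatal event above 4. It is confined to patients whose only qualifying event is a fatal SAE other than an opportunistic infection; fatal opportunistic infections and deaths after an earlier Grade 3 or 4 SAE already count.

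The counting result needs no rates: one such death can be the difference between a hold and no hold, and three or more make the mandatory hold impossible. The probability results are illustrative, and at low event rates the overall change is small. The point does not touch the primary analysis, the type I error or the sample size.

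**What to change.** In item 14, replace the two-grade range with *Grade 3 or higher SAEs, including death*. The infection limb, the threshold of 3 and the group of 5 can stay as they are.

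The cost is a few words in one sentence. Extra holds would arise only when such a death has occurred, which is when a pause for review is wanted. No change to visits, endpoints or analysis follows.

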Sample size estimation: The primary study goal is to compare the long-term efficacy of RTX (given at baseline and repeated at 6 months) with CSA (12 months treatment + 2 months taper) using proteinuria response 24 months after randomization. Proteinuria positive response will be defined as attaining and maintaining CR or PR at 24 months after randomization. We propose to establish that the RTX treatment is non-inferior to the CSA. RTX will be considered non-inferior to CSA if the response rate of the RTX arm is at most 15% worse than that of CSA arm. In addition we will compare the quality of life (QOL) and adverse event (AE) profile over the course of the treatment period. The preliminary data has indicated that CSA is effective in inducing a CR/PR of proteinuria in between 60 and 75% of MN cases.^{48, 51} However, nephrotic syndrome (NS) relapses may be as high as 50% once CSA is discontinued.⁸⁵ Thus, we estimate a CR/PR rate in patients treated with CSA of 30-50% at 24 months after randomization.⁸⁵ Similar remission and relapse rates with the use of Tacrolimus (another calcineurin inhibitor) have been reported by Praga et al.⁵⁶ In this latter study, almost half of the MN patients had a relapse of the nephrotic syndrome after tacrolimus was discontinued.⁵⁶ On the other hand, based on the long term follow up on the 35 patients treated with RTX from our 2 studies, we estimate the relapse rate to be <10% at 24 months.^{71, 75} We observed a CR/PR rate at 12 months, very similar to the rate for calcineurin inhibitors i.e. 60%, and in our second study completed recently, we observed an 80% CR/PR rate at 24 months, implying that RTX had a ~20% failure rate with 95% (CI 6% to 44%). To be conservative for the sample size estimation, we considered a maintained CR/PR rate at the low end of our previous experience, 55% CR/PR for RTX at 24 months and at the high end of our experience with CSA (CNI therapy) CR/PR for CSA of 45%. We propose a non-inferiority trial with non-inferiority margin $\delta = 15\%$, with the null hypothesis of $\pi_{RTX} - \pi_{cyclosporine} < \delta$, where π_{RTX} and $\pi_{cyclosporine}$ are the proportions of patients with CR/PR at 24 months in treatment arms of RTX and CSA, respectively. Under these assumptions, and a one sided alpha of 0.025, enrollment of 63 evaluable patients per study arm is required to achieve 80% power to show that the RTX is not inferior. For the intent to treat (ITT) analysis we will consider all patients lost to follow up to be non-responders so no correction to the sample size is needed for dropouts. With 63 patients per arm we will have 80% power to detect moderate differences of .6 standard deviations for continuous measures or around .25 for proportions for the comparisons of the QOL and AEs.

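### The printed null hypothesis puts the non-inferiority boundary at +15 points, while the rule in words and the sample size put it at −15 points

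*Combined protocol and SAP*

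**What the plan says.** All the relevant text is in the combined protocol and SAP, under Statistical Methods and Analysis, in the paragraph headed Sample size estimation.

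- Rule in words: "RTX will be considered non-inferior to CSA if the response rate of the RTX arm is at most 15% worse than that of CSA arm".
- Margin, given as a positive number: "We propose a non-inferiority trial with non-inferiority margin $\delta = 15" (per cent).
- Rule in symbols, introduced by "with the null hypothesis of" and reading in full: "with the null hypothesis of $\pi_{RTX} - \pi_{cyclosporine} < \delta". The paragraph defines the two π as the proportions of patients with CR/PR at 24 months in the RTX and CSA arms, so a larger π is better.
- Planning rates: "55% CR/PR for RTX at 24 months" and "CR/PR for CSA of 45" (per cent).
- Error rate: "a one sided alpha of 0.025".
- Result: "enrollment of 63 evaluable patients per study arm is required to achieve 80% power to show that the RTX is not inferior".

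The next paragraph, Statistical and Analytical Plan, names a logistic regression test for the primary endpoint and does not mention the 15% margin. The Overview and Specific Aim 1 state the non-inferiority aim without a margin.

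**The concern.** For a success proportion, a non-inferiority null says that the new treatment is worse by the margin or more: π_RTX − π_CSA ≤ −δ. The printed null has +δ on the right-hand side. It therefore contains RTX equal to CSA, and RTX 14 points better than CSA, as cases still to be disproved. Rejecting it would establish superiority by more than 15 points, which is not the trial's stated aim.

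Recoding the endpoint does not rescue the line. If π were the proportion failing, the non-inferiority null would be π_RTX − π_CSA ≥ +δ, and the printed inequality would be the alternative. The coding matters here because the analysis paragraphs call the primary endpoint urine protein failure, while the sample size paragraph works with CR/PR.

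At stake is the threshold for the primary conclusion. This paragraph holds the only margin in the plan and the only formal statement of the null. A result such as the planned +10 points would meet the rule in words and fail the rule in symbols. If the sign were corrected only after the data had been seen, the correction could look post hoc.

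**Working it through.** **Inputs** (all from Sample size estimation): RTX 55%, CSA 45%, margin 15 points, one-sided α = 0.025 (z = 1.96), power 80% (z = 0.8416), 63 per arm. The normal approximation with unpooled variance is my assumption, because the plan does not name its formula.

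**1. Reproduce the plan's sample size with the boundary at −15 points.**

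n per arm = (1.96 + 0.8416)² × (0.55×0.45 + 0.45×0.55) / (0.10 + 0.15)²
= 7.849 × 0.495 / 0.0625 = 62.2, rounded up to **63**. This matches the plan.

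Variants do not match: one-sided 0.05 gives 49, 90% power gives 84, and a continuity correction gives about 71.

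**2. Power at 63 per arm with the boundary at −15 points.**

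SE = √(0.495/63) = 0.0886

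Power = Φ((0.10 + 0.15)/0.0886 − 1.96) = Φ(0.86) = **80.5%**. With a pooled null variance it is 80.2%, and by exact enumeration of the Wald test 80.5%.

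**3. The same calculation with the printed boundary, +15 points.**

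Chance of rejection = Φ((0.10 − 0.15)/0.0886 − 1.96) = Φ(−2.52) = **0.58%** (0.56% pooled; 0.85% exact).

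The planned difference of +10 points lies inside the printed null, so this is a rejection rate when that null is true. No sample size could give 80% power against the +15 boundary at these rates, because the assumed difference is below it. The plan's 63 therefore cannot have been derived from the printed line.

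**4. Observed difference needed** (SE at the planning rates).

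| Boundary | Calculation | Observed RTX − CSA must exceed |
|---|---|---|
| −15 points (words) | −0.15 + 1.96 × 0.0886 | about +2.4 points |
| +15 points (symbols) | +0.15 + 1.96 × 0.0886 | about +32 points |

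Any observed result between about +2.4 and +32 points gives opposite conclusions under the two statements.

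**5. How far the printed line is from the design.** With illustrative true rates of 60% v 30%, SE = √((0.24 + 0.21)/63) = 0.0845, and the printed null is rejected with probability Φ((0.30 − 0.15)/0.0845 − 1.96) = 43%. With CSA at 45%, RTX would need a true rate of about 83% for 80% power against the printed null.

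**The case against.** The strongest reply is that nobody would act on the printed sign. The decision rule is stated correctly in words in the same paragraph, the study hypothesis and Aim 1 call for non-inferiority, and the sample size follows only from −15 points. A careful statistician would probably infer the intent. This stands, and it limits the severity. It does not remove the contradiction. The sentence in words also leaves open whether at most 15% worse refers to the point estimate or to a confidence limit, which a formal hypothesis is meant to settle.

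A second reply is that an analyst following the Statistical and Analytical Plan would not program +15 points, because the logistic test named there uses no margin of either sign. That is correct. It also means that the analysis paragraph cannot supply the right boundary. Whether that test addresses non-inferiority at all is a separate question, and this point does not rest on it.

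A third reply is that the text was read from PDF by a program, so a minus sign before δ may have been lost. This cannot be excluded. The subtraction sign in the same expression did survive, but only the original page can settle it.

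A reader might infer from the 0.6% that the trial is underpowered, with 0.6% in place of 80%. The documents do not support that. The 80% belongs to the rule in words, for which it is correct. The 0.6% is the rejection rate of a hypothesis that the trial was not designed to test.

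**Conclusion.** Wrong as written: an internal inconsistency in the primary decision threshold. The two statements of the boundary differ by 30 points (−15 v +15), which moves the observed difference needed for success from about +2.4 to about +32 points at the planning rates. The planned 63 per arm and 80% power are correct, and only the printed hypothesis needs to change. The conclusion rests on the π being CR/PR proportions and δ being positive, both of which the paragraph states, and on the printed line being free of an extraction error. The numerical results assume the planning rates of 55% and 45% and a normal approximation; the pooled and exact versions lead to the same conclusion.

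**What to change.** First check the original page for a minus sign before δ. If it is there, the null already has the right sign, and only the confidence-interval rule below needs adding. If it is not, replace the printed null with:

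- H0: π_RTX − π_CSA ≤ −0.15
- H1: π_RTX − π_CSA > −0.15

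where π is the proportion with CR or PR at month 24.

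In either case, state the rule operationally: conclude non-inferiority when the lower limit of the two-sided 95% confidence interval for RTX minus CSA in month-24 CR/PR exceeds −15 percentage points. This matches the one-sided 0.025 used for the sample size. Repeat the rule in the Statistical and Analytical Plan, expressed for CR/PR, so that the failure coding used there cannot reverse the sign.

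The cost is a few lines of wording, made before the outcome data are analysed. Sample size, patients and data collection do not change.
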